Regardless of randomization, at this point the ECV procedure proceeds using normal routine. Once completed, all patients will mark a line on a 100mm VAS to assess post-ECV pain. The ECV will be attempted up to four times and VAS will be assessed after each attempt.

The research physician will then remove the Fetal Pillow and perform a post procedural ultrasound to verify fetal position. Regardless of randomization, the procedure is completed per the usual routine of fetal monitoring, assessing for labor or bleeding, discussing post-procedure care, then discharge home (or, less likely, admitting for either observation or delivery).

The researcher will fill out the ECV portion of the data collection form.

Visit 2 (Labor and Delivery): There are no study interventions during this visit. The file linking the subject's FIN and study numbers will be sent to the honest broker who will then extract the data for delivery outcomes for the mother and neonate along with the final cost calculations. This data will be entered into a spreadsheet by the honest broker and then sent back to the research team. The research team will send the file linking the subject's FIN and study numbers at the intervals outlined in the safety monitoring plan (first 10 randomized subjects and every 20 subjects thereafter). The investigators are unblinded to patient randomization after the ECV procedure has been completed and during data collection for delivery and neonatal outcomes.

Data collection for patients delivering outside of AdventHealth facility. Patients will sign a release of records; study coordinator will request records from delivering facility and delivery outcomes data will be imported into spreadsheet linked to FIN.

Study Duration:

Estimated date of study completion: March 31, 2023

- Projected start date: November 1, 2020.
- Projected completion of enrollment of all study subjects: November 1, 2022.
- Projected final data collection date: March 1, 2023.

Materials of Human Origin: N/A

Study Outcome Measures (Endpoints)

Primary Outcome:

Proportion of patients undergoing ECV who have a successful outcome with and without an inflated Fetal Pillow.

Secondary Outcomes:

As noted, many of these data points are normally recorded in the medical record during an ECV procedure and subsequent delivery, regardless of study participation.

Subject Information (maternal):

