Clinical trial monitoring is conducted to ensure that the rights and well-being of trial participants are protected. Reported trial data are accurate, complete and verifiable.

Clinical trial monitoring will be conducted by AdventHealth Office of Research Integrity monitoring team to ensure compliance with all applicable federal and state regulations, ICH GCP E6 (R2) standards and approved protocol. This study will be monitored using a risk-based approach. A monitoring plan will be created to ensure patient safety, data quality and integrity is ongoing throughout the life of the study. The frequency and elements of monitoring will be outlined in the monitoring plan. The monitor will ensure study is conducted, recorded and reported as required by federal regulations and IRB of record. Monitoring will be conducted on-site and/or remote. After completion of site monitoring, a report will be provided to PI and study team. The PI and study team are required to review the report and work on significant findings or discrepancies to resolution. If any findings are required to be reported to the IRB, the PI will be made aware and prompted to self-report. All serious and continuing non-compliance is shared with the Research Oversight Committee who may require appropriate actions.

Protocol Deviations

All deviations and SAEs must be reported promptly to AH ORI and regulatory team. SAEs must be reported within 24 hours of discovery. Any SAE required to be reported to the FDA and IRB will be completed with the assistance of the central regulatory team in conjunction with the principal investigator and study team.”

Data Sharing (outside of AdventHealth Orlando): N/A

Sample Size Determination

Based on prior studies of patients without regional anesthesia who had a success rate of approximately 49%, and assuming a 1:1 allocation of intervention and control subjects, with an 80% power, and a 2-sided 5% significance level, we calculated a sample of size of 69 in each group to increase the success rate from 49% to 73.5%. Assuming a 10% case dropout rate we will enroll 76 patients in each arm (152 total participants).

Statistical Analysis Plan

Primary Objective Analysis

The success of ECV procedures for the intervention group compared to the control group will be analyzed using chi-square and Fisher exact tests. A P value of <0.05 will be considered statistically significant.

Secondary Objective Analysis

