Patient requests withdrawal: Patients who request withdrawal for any reason will be immediately withdrawn. If a patient initially consents to have the Fetal Pillow placed, then changes her mind before or during the procedure, the researcher will remove the device and offer the patient the opportunity to proceed with an ECV attempt off-protocol. Researchers will ask the patient if they can complete data collection for delivery and proceed according to the patient's wishes. There are no known or suspected harms from withdrawing from the study.

Data Collection and Follow-up for Withdrawn Subjects

Patients electing to withdraw from the study will be asked if they consent to data collection for delivery. If they decline this, then data collection will discontinue, and the data collection sheet will be stored as deidentified data in case the patient's reason for withdrawal (for example, excessive pain) is identified as a side effect of the device. The percentage of patients withdrawing and the reasons for withdrawal will be calculated and included in any manuscript submissions.

Adverse Event Reporting

Adverse events will be collected from the time of insertion up to 1 hour after the ECV procedure and followed until discharge. Adverse events such as excessive pain or bleeding will be recorded as part of the data collection. Adverse events of special interest will be reported according to AdventHealth Orlando IRB policies

Adverse events of special interest include:

Term	Mild	Moderate	Severe	Serious	Serious
------	------	----------	--------	---------	---------

Vaginal Hemorrhage	Mild symptoms; intervention not indicated	Moderate symptoms; intervention indicated	Transfusion indicated; invasive intervention indicated; hospitalization	Life-threatening consequences; urgent intervention indicated	Death
Pelvic Hematoma	Mild symptoms; intervention not indicated	Minimally invasive evacuation or aspiration indicated	Transfusion; invasive intervention indicated	Life-threatening consequences; urgent intervention indicated	Death
Vaginal Laceration	Separation of the perineal skin only	Injury to the perineal muscles but not the sphincter or rectum	Injury to the perineal muscles and anal sphincter	Injury to the perineal muscles, sphincter, and rectal mucosa	Death

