A serious adverse event is defined as an adverse event “if, in the view of the investigator, it results in any of the following outcomes: Death, a life-threatening adverse event, inpatient hospitalization or prolongation of existing hospitalization* a persistent or significant incapacity or substantial disruption of the ability to conduct normal life functions, or a congenital anomaly/birth defect. Important medical events that may not result in death, be life-threatening, or require hospitalization may be considered serious when, based upon appropriate medical judgment, they may jeopardize the patient or subject and may require medical or surgical intervention to prevent one of the outcomes listed in this definition.

*Planned hospitalization for a pre-existing condition, or a procedure required by the clinician that is not related to the device, will not be considered a Serious Adverse Event.

Only SAEs deemed related to the device will be reported electronically to the FDA and AHIRB no later than within 10 working days after the investigator first learns of the event (21 CFR 812.150(a)(1)).

Safety Monitoring Plan

Safety Monitoring

While we consider the project to be relatively low risk, there is always the possibility of adverse events. The safety monitoring plan will include: (1) review of interim analyses of outcome data; (2) review of reports of related studies to determine whether the monitored study needs to be changed or terminated; (3) review of major proposed modifications to the study prior to their implementation; and (4) provide the study leadership with written recommendations concerning the trial including continuing, changing or terminating the study. Safety monitoring will occur after the first 10 randomized subjects and every 20 subjects thereafter. [name] M.D., Chair of Fetal Medicine Department and [name] R.N., Nurse Manager Labor and Delivery Unit will conduct the safety monitoring plan.

Data and Safety Monitoring Board (DSMB) or Equivalent: N/A

Ethical Considerations

N/A

Sharing of Results with Subjects

Patients will be immediately aware if the ECV procedure was successful. Upon completion of study data analyses, subjects will have the option to contact study team to obtain their randomization arm information.

Funding Source

There is no external funding for this research. The manufacturer of the Fetal Pillow has agreed to supply devices and have not been involved in the study design.

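### Adverse event collection closes 1 hour after ECV and SAEs have no window of their own, so serious events up to and at delivery have no clear reporting status, and their planned retrieval is batched about three months apart

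*Combined protocol and SAP*

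**What the plan says.** - **Collection window (Adverse Event Reporting).** "Adverse events will be collected from the time of insertion up to 1 hour after the ECV procedure", with follow-up until discharge. The natural reading is that events already collected are followed to discharge, not that new ones are collected until then.
- **SAE definition (Serious Adverse Event Reporting).** "A serious adverse event is defined as an adverse event" that leads to one of a list of outcomes, such as death or hospitalization. No separate period is given.
- **Reporting clocks.** Protocol Deviations: "SAEs must be reported within 24 hours of discovery". Serious Adverse Event Reporting: "Only SAEs deemed related to the device will be reported electronically to the FDA and AHIRB no later than within 10 working days", counted from when the investigator first learns of the event. Neither sets a limit on when the event must have begun.
- **Usual course (Study Visits, Visit 1).** Most women are expected to go home after the procedure. Admission is described as the less likely course.
- **Late outcomes (Secondary Outcomes).** Stillbirth, with the gestational age at which it occurred, is listed for collection. So are placental abruption and NICU admission.
- **Retrieval (Study Visits, Visit 2).** An honest broker extracts delivery and neonatal outcomes once the team sends the linking file, "at the intervals outlined in the safety monitoring plan (first 10 randomized subjects and every 20 subjects thereafter". The Safety Monitoring Plan uses the same schedule: "Safety monitoring will occur after the first 10 randomized subjects and every 20 subjects thereafter". No DSMB is planned.
- **Deliveries elsewhere.** Visit 2 has the coordinator request the outside records, with no timing. Early Withdrawal of Subjects removes these women from the analysis.

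**The concern.** The device is used off-label, and the Background section accepts that it might cause unforeseen harm to mother or fetus. The outcome lists show that the sponsor expects serious harm could come to light at delivery, but the adverse event rules stop well before most deliveries. Recording a stillbirth as an outcome in a spreadsheet is not the same as assessing it for relatedness and reporting it as a safety event. If the planned extraction is how the team learns of it, up to 20 more women could be randomized first. All of them would have the device inserted and, under 1:1 allocation, about half would have it inflated.

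**Working it through.** **1. What is covered, reading the sections together**

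| Timing of a serious event | Collected as an adverse event? | Planned way for the team to learn of it |
|---|---|---|
| Insertion to 1 hour after ECV | Yes | Direct observation |
| After 1 hour, before discharge from the ECV visit | Not on a plain reading | None stated as safety collection |
| After discharge, delivery in the system | Not on a plain reading | Batched extraction |
| After discharge, delivery elsewhere | Not on a plain reading | Records request, no timing |

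The gap therefore opens at 1 hour, not at discharge. The documents describe no contact or notification between discharge and delivery.

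Cord prolapse has a further problem. The severity table grades it under ruptured membranes, with NICU admission or fetal death in the definitions, but it is in none of the maternal, neonatal or procedural outcome lists. A batch would show it only indirectly, as a stillbirth, NICU admission or cesarean.

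**2. The plan's own totals**

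Inputs from Sample Size Determination: 49% versus 73.5%, 80% power, two-sided 5%, 10% dropout.

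- Normal approximation for two proportions: n = [1.96 × √(2 × 0.6125 × 0.3875) + 0.8416 × √(0.49 × 0.51 + 0.735 × 0.265)]² / 0.245² = 60.9, so 61 per arm.
- With continuity correction: (60.9/4) × [1 + √(1 + 4/(60.9 × 0.245))]² = 68.8, so 69 per arm. This reproduces the stated figure.
- Dropout: 69 × 1.10 = 75.9, so 76 per arm and 152 in total. Dividing by 0.90 would give 77 per arm.
- Study Site/Location and Number of Subjects states 138, which is 2 × 69. Both totals are carried forward.

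**3. Time between batches**

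The documents give no accrual rate or calendar interval. Study Duration gives a start of November 1, 2020 and "Projected completion of enrollment of all study subjects: November 1, 2022". That is 730 days, or 730/30.4375 = 23.98 months. Uniform accrual is assumed.

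| Quantity | N = 152 | N = 138 |
|---|---|---|
| Accrual, N/23.98 | 6.34 per month | 5.75 per month |
| First batch, 10/rate | 1.6 months | 1.7 months |
| Between later batches, 20/rate | 3.16 months (96 days) | 3.48 months (106 days) |
| Average wait, half the interval | 1.6 months | 1.7 months |
| Subjects after the last scheduled review (10, 30, 50, …) | 152 − 150 = 2 | 138 − 130 = 8 |

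**4. Sensitivity to accrual**

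At half the planned rate the interval is 6.3 to 7.0 months. At 1.5 times the rate it is 2.1 to 2.3 months. For a woman undelivered when her batch is cut, the wait lengthens, because the plan does not say when her record is pulled again.

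**The case against.** The strongest reply is that the reporting rules do not depend on the collection window. Both clocks start at discovery, the SAE definition turns on outcome, and the definition of an unanticipated adverse device effect has no time limit. The device is removed before the woman goes home, so a short window for routine events is reasonable. Late harms are prespecified outcomes, and the safety monitoring includes review of interim outcome data.

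Much of this stands, and it rules out several stronger readings that a reader might infer:

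- **That a late stillbirth can never start the SAE clock, or that the reporting rules do not apply to it.** No section says so. What the text lacks is any statement that such an event counts as an SAE, while the definition ties SAEs to adverse events and their collection ends at 1 hour.
- **That a three-month wait replaces a 24-hour one.** The first runs from event to discovery, the second from discovery to report. The protocol never promised knowledge within 24 hours of onset.
- **That the batch is the only way the team could learn of an event.** It is the scheduled route for deliveries in the system. Study Outcome Measures also has researchers recording delivery outcomes from the medical record, outside records are requested separately, and the monitoring plan is a separate document not seen here. None of these secures prompt detection.
- **That three months is the typical delay.** It is about the longest wait between batches. The average is about half of it.

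The objection does not remove the point. If late SAEs are outside collection, serious harm may go unreported. If they are inside, the text does not say so, and a clock that starts at discovery protects little when discovery is batched. Blinding does not explain the delay either, since Visit 2 unblinds the investigators once the ECV is complete.

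**Conclusion.** The concern holds as a gap in scope and a possible delay in discovery. On a plain reading, serious maternal, fetal or neonatal events beginning more than 1 hour after ECV are not collected as SAEs, including those before discharge. The most generous reading leaves their status ambiguous. The scheduled retrieval of in-system delivery data can delay discovery by up to about 3.2 to 3.5 months between batches, or 1.6 to 1.7 months on average.

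These figures assume uniform accrual over the projected 24 months, totals of 138 to 152, and no earlier notice by another route. The primary analysis is unaffected. The protocol should be amended because the matter concerns fetal safety with an off-label device and the remedy is modest.

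**What to change.** 1. **Adverse Event Reporting and Serious Adverse Event Reporting:** keep the 1-hour window for non-serious events. State that SAEs in mother, fetus and newborn are collected through the delivery discharge and fall under the existing clocks that run from discovery.
2. **Study Visits, Visit 2:** extract stillbirth, abruption and NICU admission per delivery, or at a short fixed interval, and not only at the 10- and 20-subject batches. Without this step, a longer window would not speed discovery.
3. **Secondary Outcomes:** add cord prolapse to the delivery data items.
4. **Visit 2 and Early Withdrawal of Subjects:** reconcile the two on outside deliveries so that these women stay in safety follow-up.

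The cost is more than a change of wording: the honest broker and coordinator would make more frequent small data pulls, and some SAEs unrelated to the device would be reported internally. The burden is limited because delivery records are already collected and only device-related SAEs go on to the FDA and IRB.

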3. EGA
4. Name of obstetrician performing ECV procedure
5. Presence of inflated Fetal Pillow
6. Presence of terbutaline
7. Presence of palpable fetal head
8. Estimated fetal weight (kg)
9. Fetal head position *confirmed by ultrasound
10. Fetal back position
11. Position of fetal neck
12. Location of placenta
13. Amniotic fluid index (4 quadrant total)
14. Fetal station (-3 through +3)
15. Maternal cervical dilation (cm)
16. Presence of rupture of membranes within 1 hour of procedure
17. Presence of 3 or more contractions in 10 minutes immediately prior to procedure
18. Bleeding equal to a menstrual period during or within 1 hour of the ECV procedure.
19. Development of a pelvic hematoma during or within 1 hour after the ECV procedure.
20. Development of a vaginal laceration during insertion of the device, the ECV procedure, or removal of the device.
21. Presence of fetal bradycardia
22. Presence of fetal heart rate decelerations
23. Presence of delivery within 1 hour of procedure
24. VAS pain score immediately prior to ECV (-3 minutes)
25. VAS pain score immediately after insertion of Fetal Pillow (+ 2 minutes)
26. VAS pain score after inflation/sham inflation (+ 1 minute)
27. VAS pain score immediately after each ECV procedure attempt, maximum of 4 attempts (+ 2 minutes)
28. Total number of attempts
29. Procedure successful Y N (Primary Outcome) *confirmed by ultrasound
30. Fetal head position post ECV *confirmed by ultrasound
31. Number of forward rolls
32. Number of reverse rolls
33. Note which procedure was successful

34. Did patient request to have spinal or epidural anesthesia after initiation of ECV procedure (off of study protocol): Y N
35. Presence of regional anesthesia prior to ECV procedure (Excluded from study)
36. Length of time from start of procedure to hospital discharge
37. Cost of hospital stay for ECV procedure

Study Design

Research Design

This is a prospective, randomized double-blind clinical trial evaluating the effect of a balloon device to elevate the fetal buttocks during external cephalic version procedures. Eligible study population: pregnant women between 37-40 weeks estimated gestational age with a breech presenting baby and no contraindications to ECV.

Study Agent, Device, and/or Intervention Description:

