Visit 1 (ECV Procedure): The PI/Sub-I will meet the patient at the labor and delivery area, and review both the ECV procedure and possible study inclusion. The patient and researcher will sign consent forms if the patient qualifies for study inclusion and agrees to participate.

After weighing the patient, calculating a body mass index, performing a digital cervical exam, and performing a fetal non-stress test and obstetric ultrasound, all routine components of the ECV process, the PI/Sub-I will verify there are no exclusion criteria. Assuming that an ECV is still necessary and safe, the patient will receive a 0.25mg subcutaneous injection of terbutaline, a medication to quiet the uterus that is commonly used for ECV procedures. The midwife/physician performing the device inflation or sham inflation will open the randomization envelope. The researchers are blinded to patient randomization. All patients will mark a line on a 100mm VAS to assess pre-procedure pain.

The researcher will show the patient the device, open the sterile container, and insert the device into the vagina per manufacturer's guidelines for all patients in the study. All patients will mark a line on a 100mm VAS to assess post-insertion pain. The study physician will then obtain the assistance of a trained midwife/physician to inflate the device or perform a sham inflation. For the physician to remain blinded, the physician will leave the room during the time of the inflation/sham inflation. This will be documented in the source documents. Midwives/Physicians performing the inflation or sham inflation will have undergone previous training. Inflating the

Fetal Pillow is similar, although less difficult, than other balloon devices commonly used on the labor and delivery unit. The assisting midwife/physician will inflate the device with 180 mL of saline for those patients randomized to inflation. This will occur under a sheet so that the patient is blinded to the randomization scheme. If the patient is randomized to no inflation, the midwife/physician will perform a sham inflation, also under a sheet. All patients will mark a line on a 100mm VAS to assess post-inflation/sham inflation pain. The assisting midwife/physician then leaves the room, and the study physician reenters the room and proceeds with the ECV procedure.

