Maternal and neonatal outcomes will be analyzed using chi-square and Fisher exact tests for categorical variables, unpaired t-tests for continuous variable, and non-parametric tests for continuous variables that are not normally distributed. P values <0.05 will be considered statistically significant.

Potential Risks and Benefits

Potential Benefits

The Fetal Pillow device may improve the ECV success rate.

Potential Risks

Although unlikely based on prior device usage during 2nd stage arrest, it is possible the device may cause vaginal bleeding, increased pain during the procedure, or either no change in success or a lower success rate compared to performing the procedure without the device. Terbutaline administration may cause maternal tachycardia, irritability, chest pressure or chest pain. While loss of confidentiality is a potential risk to patients, patient information will be de-identified prior to analysis and only study personnel will have access to patient information. The United States Food and Drug Administration has determined that this study protocol is a nonsignificant risk (NSR) study (Review # Q191927, notification received December 18, 2019).

Mitigation of Risks

Patients will be asked prior to administration of terbutaline if they have contraindications, which is standard practice prior to using this medication.

Provisions to Protect the Privacy Interest of Subjects

The steps to protect the privacy of subjects have been described previously. Briefly, study documentation and patient information will be stored in a separate file on a password-protected laptop stored in a locked office. Drs. [name], [name] and research team will have access to both files.

Early Withdrawal of Subjects

Investigator Withdrawal of Subjects.

Inability to place Fetal Pillow: If the Fetal Pillow cannot be placed, for example due to pain, or the Fetal Pillow cannot be inflated, the patient will be withdrawn from the study. However, she may undergo an attempted ECV outside of the study protocol if she wishes.

Delivery at a hospital outside of the AdventHealth Orlando system: If the patient delivers outside of the AdventHealth Orlando system she will be withdrawn from the study analysis.

Subject Request for Withdrawal from Study

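### Adverse event collection opens at device insertion, after the protocol-specified terbutaline injection, so non-serious drug reactions before insertion go uncounted (minor)

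*Combined protocol and SAP*

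**What the plan says.** Adverse Event Reporting sets the collection window: "Adverse events will be collected from the time of insertion up to 1 hour after the ECV procedure and followed until discharge".

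Study Visits, Visit 1 (ECV Procedure), puts the injection earlier. After consent, the routine examinations and the check of exclusion criteria, "the patient will receive a 0.25mg subcutaneous injection of terbutaline". The opening words of that sentence make the step conditional: "Assuming that an ECV is still necessary and safe, the patient will receive". The text then continues: "The midwife/physician performing the device inflation or sham inflation will open the randomization envelope", and "All patients will mark a line on a 100mm VAS to assess pre-procedure pain". Only after this is the device shown, unpacked and inserted, in both arms.

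Potential Risks includes the drug among the hazards of taking part: "Terbutaline administration may cause maternal tachycardia, irritability, chest pressure or chest pain". Mitigation of Risks adds: "Patients will be asked prior to administration of terbutaline if they have contraindications". Procedural Outcomes, item 6, records "Presence of terbutaline" as a data item.

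**The concern.** The protocol specifies a drug, names its reactions as study risks, and then begins counting adverse events at a later step. Every woman who is injected passes through a consented, drug-exposed interval in which the stated rule collects nothing.

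The omission matters most for a woman who reacts and goes no further. If the investigator stops the visit before insertion, she never reaches the point at which collection begins. Her envelope may already be open, so she can count as randomized with no adverse event record. Both the safety monitoring, which runs by number of randomized subjects, and the published safety table would then show fewer drug reactions than occurred.

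**Working it through.** No arithmetic applies. The plan states no figure on this point, and the question is one of sequence and coverage.

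**Sequence in Visit 1, set against the window**

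| Step | Inside the adverse event window? |
|---|---|
| Consent, examinations, exclusion check | No |
| Terbutaline injection | No |
| Envelope opened | No |
| Pre-procedure pain score | No |
| Device shown and unpacked | No |
| Device insertion | Window opens |
| Post-insertion pain score, inflation or sham, ECV attempts | Yes |
| Up to 1 hour after ECV | Yes, then window closes |

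The uncovered, drug-exposed stretch runs from the second row to the sixth. The documents give no duration for it.

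**Could another data item record the reaction?** The Procedural Outcomes list and the paragraph on the outcome of the ECV procedure cover bleeding, hematoma, laceration, membrane rupture, contractions, labor, fetal heart rate, early delivery and pain scores. Neither has an entry for maternal tachycardia, irritability, chest pressure or chest pain. Recording these therefore depends on general adverse event collection.

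**Could another reporting route catch it?**

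1. Serious events. Protocol Deviations requires serious adverse events to be reported within 24 hours of discovery and ties this to no start time. A serious reaction before insertion could be reported this way. A non-serious one would not be.
2. The woman withdraws. The withdrawal sections cover a patient who changes her mind before or during the procedure, and the proportion withdrawing and their reasons are to be published. A reaction that prompts her own withdrawal may surface there.
3. The investigator stops. The listed grounds for investigator withdrawal are failure to place or inflate the device and delivery outside the hospital system. A stop for a drug reaction before insertion is not clearly among them.
4. The reaction begins after insertion. It is inside the window and can be graded in the catch-all row of the severity table.

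Two cases remain uncovered: a non-serious reaction that resolves before insertion, and a non-serious reaction for which the investigator stops before insertion.

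**Does the gap differ by arm?** The injection is described before the envelope is opened. Until inflation or sham inflation the two arms receive the same steps, and the study physician and patient are blinded. Nothing in the uncovered interval depends on the device being inflated.

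**Causality scale.** The relatedness table in the adverse event section is defined by reference to the device alone. Even a terbutaline reaction inside the window has no category that attributes it to the drug.

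**The case against.** The strongest reply is one of scope. The trial evaluates a device, the Visit 1 text describes terbutaline as a common part of ECV, and the causality scale concerns the device. Opening the window at insertion is coherent with that purpose. This explains the choice, but the protocol itself specifies the drug and lists its reactions among the study's risks. Having done so, it should count them from when the drug is given.

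A second reply is that the gap is narrower than it looks, and this stands. A reader might infer that no reaction before insertion is ever captured. The documents do not support that, because serious-event reporting has no insertion-based start and withdrawal reasons are to be published.

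A reader might also infer that the protocol contradicts itself on who receives terbutaline, giving it to everyone in one place and asking about contraindications in another. It does not. The injection is conditional on ECV still being necessary and safe, the contraindication question comes before the drug, and item 6 allows for the drug being absent. These statements are compatible. What is missing is only what follows when a woman reports a contraindication.

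Finally, it could be feared that the gap biases the treatment comparison. The order of events and the identical handling of the arms up to inflation make that unlikely.

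**Conclusion.** The point holds in a limited form and is minor. Non-serious terbutaline reactions that resolve before insertion, or that lead the investigator to stop before insertion, lie outside routine adverse event collection. The result is an under-count of absolute harms in both arms. The primary outcome is not affected, and the comparison between arms is unlikely to be.

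The size cannot be given. The interval from injection to insertion, the reaction rate and the number of women with a contraindication are all absent from the documents. The interval applies to every woman injected, but how many would react within it is unknown.

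The conclusion rests on two assumptions: that the Visit 1 narrative is in chronological order, and that insertion in the adverse event section means insertion of the device.

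**What to change.** In Adverse Event Reporting, start collection at the terbutaline injection, as the first protocol-specified administration after consent, and keep the rest of the sentence unchanged. Optionally, add one field to the data form for relatedness to terbutaline, separate from relatedness to the device.

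The cost is one edited sentence and, if adopted, one form field. The downside is that a few more minor, expected drug effects will be recorded.

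As a clarification only, the sponsor should reconcile Procedural Outcomes item 6, the inclusion and exclusion criteria, Visit 1 and Mitigation of Risks, so that they state how a woman who reports a contraindication proceeds and how she is analysed. Which clinical rule applies is for the sponsor to decide.
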